2.1.4.3 Deaths

The deaths observation period are per the observation periods defined above.

- Death on-study: deaths occurring during the on-study observation period
- Death on-treatment: deaths occurring during the TEAE period
- Death poststudy: deaths occurring after the end of the study

2.1.4.4 Laboratory safety variables

Clinical laboratory data consist of blood analysis (including hematology clinical chemistry amylase, lipase, and lipid profile) and urinalysis. Clinical laboratory values will be summarized in both standard international units and conventional units when applicable.

Blood samples for clinical laboratories will be taken at designated visits (see study flowchart in [Appendix E](#)). The following laboratory parameters will be assessed at a central laboratory:

- Hematology
 - **Red blood cells and platelets:** hemoglobin, hematocrit, red blood cell count, platelet count,
 - **White blood cells:** white blood cell count, neutrophils, lymphocytes, monocytes, basophils, eosinophils
- Clinical chemistry
 - **Metabolism:** Glucose (serum), creatine phosphokinase (CPK),
 - **Electrolytes and minerals:** sodium, potassium, chloride, calcium, phosphorus, bicarbonate (ie, carbon dioxide), magnesium
 - **Renal function:** creatinine, blood urea nitrogen (BUN), uric acid
 - **Liver function:** total protein, Albumin, alanine aminotransferase (ALT), aspartate aminotransferase (AST), alkaline phosphatase (ALP), Lactic acid dehydrogenase (LDH), total bilirubin (TB)
- Lipid parameters (fasting):
 - Total cholesterol (TC)
 - High density lipoprotein cholesterol (HDL-C)
 - Low density lipoprotein cholesterol (LDL-C) (calculated by Friedwald equation, See [Section 2.5.1](#))
 - Non-HDL-C (calculated as the difference between TC and HDL-C),
 - Triglycerides (TG).
- Pancreatic enzymes: lipase, amylase.
- Markers of Intestinal Transit and Absorption
 - Vitamins: B6, B12, K, E and A
 - Serum folate
 - Ferritin
- Markers of bone and calcium metabolism
 - Calcium
 - 25-hydroxyvitamin D

- 1,25-dihydroxyvitamin D
- Phosphorus
- Parathyroid hormone (PTH),
- Markers of bone resorption: N-terminal telopeptide (NTX), beta-C-terminal telopeptide (β -CTX-1),
- Marker of bone formation: type 1 procollagen N-terminal (P1NP), osteocalcin

Urine samples will be collected at designated visits (see study flowchart in [Appendix E](#)). The following laboratory data will be measured at a central laboratory:

- Urine dipstick includes: specific gravity, pH, protein, blood, ketones, bilirubin, urobilinogen, nitrite, and leukocyte esterase
- Urine microscopy includes, but is not limited to: detection of formed cellular elements, casts, bacteria, yeast, parasites, and crystals in centrifuged urine sediment
- Urine albumin, calcium, phosphorus, glucose, magnesium, and creatinine

Serum glucose, UGE, calculated UACR and calculated UGCR will be presented as efficacy parameters in [Section 2.4.4](#).

- Technical formulas are described in [Section 2.5.1](#).

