### **6.1.2 Double-blind Treatment Period (Day 1 to Week 26)**

Eligible patients will be randomized on Day 1 (Visit 3). In order to qualify for randomization, patients must also demonstrate compliance during the single-blind placebo Run-in Phase based upon tablet count ( $\geq 80\%$ ) and, as assessed, at the Investigator's discretion.

Randomization will be stratified by:

- HbA1c at Screening ( $\leq 8.5\%$  and  $> 8.5\%$ )
- SBP at Screening ( $< 130$  mmHg,  $\geq 130$  mmHg).

Following randomization, patients will be treated in a double-blind manner for 26 weeks. A total of 276 patients  $\geq 18$  years of age (or  $\geq$  legal age of the majority, whichever is greater) are planned to be randomly assigned 1:1:1 to the following treatment groups:

- Placebo, given as 2 placebo tablets (identical to sotagliflozin 200 mg in appearance), once daily
- Sotagliflozin 200 mg, given as 2 tablets: 1 sotagliflozin 200 mg tablet and 1 placebo tablet (identical to sotagliflozin 200 mg in appearance), once daily
- Sotagliflozin 400 mg, given as 2 sotagliflozin 200 mg tablets, once daily.

Fasting glucose (plasma or serum) and HbA1c results will be masked to study sites and patients after randomization until study end. To prevent partial unblinding, UGE and UGCR will be masked to study sites and patients, and the central laboratory urine dipstick will not include the measurement of urine glucose.

Quantitative urine glucose, albumin, calcium, and creatinine will be measured separately at selected on-site visits by the central laboratory.

All visits will be on-site visits.

If a patient discontinues treatment with investigational medicinal product (IMP) early during the Treatment Period, the patient will have a premature end of treatment (EOT) Visit and a Follow-up Visit, 4 weeks ( $\pm 5$  days) after the last dose of IMP. In addition, every effort will be made to have all patients return to the site at the time corresponding to their scheduled visits, particularly the Weeks 26 and 52 Visits.

If a patient does not agree to site visits, he/she will be contacted by telephone to inquire about their safety status, particularly at the time of the initially scheduled end of study.

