#### 9.1.2 Secondary efficacy endpoints

The continuous secondary efficacy endpoints are:

- Change from Baseline to Week 26 in HbA1c (%) comparing sotagliflozin 200 mg versus placebo

To compare sotagliflozin 400 mg and 200 mg, respectively, versus placebo for:

- Change from Baseline in FPG at Week 26
- Change from Baseline in body weight at Week 26
- Change from Baseline in SBP at Week 12 for patients with baseline SBP  $\geq 130$  mmHg
- Change from Baseline in SBP at Week 12 for all patients
- Change in the UACR (%) from Baseline to Week 26 for patients with a UACR  $>30$  mg/g at baseline
- Proportion of patients with HbA1c  $<6.5\%$ ,  $<7.0\%$  at Week 26.

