**Table 2 - Blood safety laboratory**

Clinical chemistry	Hematology	Other blood parameters
Sodium	Complete blood count (CBC)	Lipid profile
Potassium	Differential	Total cholesterol (TC)
Chloride	Platelet count	High-density lipoprotein cholesterol (HDL-C)
Carbon dioxide (bicarbonate)	Hemoglobin	Low-density lipoprotein cholesterol (LDL-C) will be calculated by Friedwald equation
Blood urea nitrogen (BUN)	Hematocrit	Non-HDLC will be calculated as the difference between TC and HDLC
Creatinine (eGFR will be calculated*)		Triglycerides (TG)
Glucose (serum)		Markers of intestinal transit and absorptiona
Alanine aminotransferase (ALT)		Vitamins: B6, B12, K, E, A
Aspartate aminotransferase (AST)		Serum folate
Total bilirubin (TB)		Ferritin
Alkaline phosphatase (ALP)		Markers of bone and calcium metabolisma
Uric acid		Calcium
Phosphorus		25-hydroxyvitamin D
Total protein		1,25-dihydroxyvitamin D
Albumin		Phosphorus
Magnesium		Parathyroid hormone (PTH)
Creatine phosphokinase (CPK)		Markers of bone resorption: N-terminal telopeptide (NTX), beta-C-terminal telopeptide (β-CTX-1)
Lactic acid dehydrogenase (LDH)		Marker of bone formation: type 1 procollagen N-terminal (P1NP), osteocalcin
		Other chemistry tests
		Amylase
		Lipase

All assessments to be performed by central laboratory.

All assessment measured in serum.

a To be collected at Baseline (Visit 3) to Week 4 (Visit 7), and at Visits 11 and 13

\*The recommended equation for estimating eGFR from serum creatinine is the 4 variable Modification of Diet in Renal Disease (MDRD) Study equation [18, 19]. The IDMS-traceable version of the MDRD Study equation is used. Either equation below may be used based on whether the laboratory reports conventional units or Standardized International (SI) units.:

Conventional Units (for use predominantly in the US): <http://nkdep.nih.gov/lab-evaluation/gfr-calculators/adults-conventional-unit.asp>

SI Units (for use predominately outside the US): <http://nkdep.nih.gov/lab-evaluation/gfr-calculators/adults-SI-units.asp>.

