#### **11.4.3.5 Analyses of laboratory variables**

The number and percentage of patients with PCSA or by the predefined categories (if no PCSA criterion is defined) at any evaluation during the on-treatment period will be summarized for each clinical laboratory test within each treatment group. The summaries will include patients in the safety population who have at least one laboratory test performed during the on-treatment period and, when required by the definition of the abnormality, with an available baseline value and available laboratory normal ranges.

Descriptive statistics will be used to summarize the laboratory results and the changes from baseline by visit and for the last on-treatment value within each treatment group. Shift tables and other tabular and graphical methods may be used to present the results for laboratory tests of interest. Listings will be provided with flags indicating the out of laboratory range values as well as the PCSA values.

The liver function tests, namely ALT, AST, ALP, and total bilirubin, are used to assess possible drug-induced liver toxicity. The proportion of patients with PCSA values at any postbaseline visit by baseline status will be displayed by treatment group for each parameter.

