2.1.4.1 Hypoglycemia

Hypoglycemia will be identified as events recorded on the dedicated e-CRF “Hypoglycemic event information” page, and will be categorized as follows (see study protocol for further details):

Severe hypoglycemia

Severe hypoglycemia is an event requiring assistance of another person to actively administer carbohydrate, glucagon, intravenous glucose or other resuscitative actions. These episodes may be associated with sufficient neuroglycopenia to induce seizure, unconsciousness or coma.

Self-monitored plasma glucose values may not be available, but neurological recovery attributable to the restoration of plasma glucose to normal is considered sufficient evidence that the event was induced by a low plasma glucose concentration.

Severe hypoglycemia is identified in e-CRF “Hypoglycemic event information” page as those documented as,

To the question “Countermeasure Administration”, ticked the option “Subject was Not Capable of Treating Self and Required Assistance”, and

To the question “Were Symptoms Present”, ticked “Yes”.

Documented symptomatic hypoglycemia

Documented symptomatic hypoglycemia is an event during which typical symptoms of hypoglycemia accompanied by a measured plasma glucose concentration of ≤ 3.9 mmol/L (≤ 70 mg/dL).

Clinical symptoms that are considered to result from a hypoglycemic episode are eg, increased sweating, nervousness, asthenia/weakness, tremor, dizziness, increased appetite, palpitations, headache, sleep disorder, confusion, seizures, unconsciousness, or coma.

Documented symptomatic hypoglycemia is identified in e-CRF “Hypoglycemic event information” page as those documented as,

1. To the question “Countermeasure Administration”, NOT ticked the option “Subject was Not Capable of Treating Self and Required Assistance”, and
2. To the question “Were Symptoms Present”, ticked “Yes”, and
3. With a plasma glucose value before countermeasure ≤ 3.9 mmol/L (≤ 70 mg/dL).

Asymptomatic hypoglycemia

Asymptomatic hypoglycemia is an event not accompanied by typical symptoms of hypoglycemia but with a measured plasma glucose concentration ≤ 3.9 mmol/L (≤ 70 mg/dL).

Asymptomatic hypoglycemia is identified in e-CRF “Hypoglycemic event information” page as those documented as,

1. To the question “Countermeasure Administration”, NOT ticked the option “Subject was Not Capable of Treating Self and Required Assistance”, and
2. To the question “Were Symptoms Present”, ticked “No”, and

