2.4.5 Analyses of safety data

The summary of safety results will be presented by treatment group. The safety data will be summarized for the 26-week core treatment period and the 52-week entire treatment period separately, unless otherwise specified.

The “observation period” defined in [Section 2.1.4](#) is applicable in all safety analyses for the classification of AEs, determination of treatment-emergent PCSA values and the last on-treatment value for the laboratory, vital sign and ECG.

General common rules

All safety analyses will be performed on the safety population as defined in [Section 2.3.2](#), unless otherwise specified, using the following common rules:

- Safety data in patients who do not belong to the safety population (eg, exposed but not randomized) will be listed separately
- The baseline value (with the exception of serum creatinine and eGFR) is defined as the last available value before the first dose of double-blind IMP. For serum creatinine and eGFR, the baseline value is defined as the average of all values before the first dose of double-blind IMP.
- PCSA values are defined as abnormal values considered medically important by the Sponsor according to predefined criteria/thresholds based on literature review and defined by the Sponsor for clinical laboratory tests, vital signs, and ECG ([Appendix B](#))
- PCSA criteria will determine which patients had at least 1 PCSA during the treatment-emergent adverse event period, taking into account all evaluations performed during the treatment-emergent adverse event period, including nonscheduled or repeated evaluations.

The number of all such patients will be the numerator for the treatment-emergent PCSA percentage.

- The treatment-emergent PCSA denominator by group for a given parameter will be based on the number of patients assessed for that given parameter in the treatment-emergent adverse event period by treatment group on the safety population.
- For laboratory parameters cited in the protocol as efficacy endpoints (including HbA1c and plasma glucose etc), PCSA summaries will not be provided. These parameters will be summarized in efficacy [Section 2.4.4](#).

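### The SAP gives conflicting instructions on whether low central-laboratory glucose is tabulated by arm as a safety result

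*SAP*

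**What the plan says.** SAP 2.1.4.4 names serum glucose twice. It is in the clinical chemistry list of central-laboratory safety tests, under metabolism. It then returns in the closing sentence: "Serum glucose, UGE, calculated UACR and calculated UGCR will be presented as efficacy parameters in" Section 2.4.4. The common rules in SAP 2.4.5 add: "For laboratory parameters cited in the protocol as efficacy endpoints (including HbA1c and plasma glucose etc), PCSA summaries will not be provided". They refer those parameters to Section 2.4.4 as well.

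Other text keeps serum glucose in the safety analysis. SAP 2.4.5.4 takes the groups of 2.1.4.4, gives summary statistics for all laboratory variables, and reports the incidence of the Appendix B abnormalities over the treatment-emergent (TEAE) period. Appendix B has a glucose row whose low criterion is ≤3.9 mmol/L and below the lower limit of normal (LLN). Protocol Table 2 lists serum glucose in the blood safety laboratory. Protocol 11.4.3.5 promises the number and percentage of patients with a PCSA "at any evaluation during the on-treatment period will be summarized for each clinical laboratory test within each treatment group". Protocol 11.4.3 drops PCSA criteria only for parameters that the protocol does not cite as safety parameters.

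The only blood glucose efficacy endpoint is fasting plasma glucose (FPG); protocol 9.1.2 lists "Change from Baseline in FPG at Week 26".

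On how low values become known, protocol 6.1.2 says: "Fasting glucose (plasma or serum) and HbA1c results will be masked to study sites and patients after randomization until study end". SAP 2.1.4.1 says: "Hypoglycemia will be identified as events recorded on the dedicated e-CRF" page for hypoglycaemic events.

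**The concern.** The closing sentence of SAP 2.1.4.4 takes a test that the protocol calls a safety test and sends it to a section where nothing is planned for it. Read together with the exclusion in 2.4.5, it invites a programmer to leave out the Appendix B low-glucose count, which the protocol requires.

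Hypoglycaemia is a stated safety endpoint, background insulin is allowed, and the protocol asks for weekly laboratory monitoring in the first 4 weeks. Central-laboratory glucose is the one source on low glucose that does not depend on a patient measuring or noticing it. Sites cannot pass it on, because they are masked to it and the central-laboratory glucose alerts described in protocol 8.2.1 and 9.1.4.7 concern high values only. If the laboratory table is not made, these values do not enter the between-arm safety comparison.

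**Working it through.** No sample size, power or alpha figure enters this point. The check is a trace of the text and a visit count.

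**Trace of serum glucose**

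| Place | Treatment of serum glucose | Points to |
|---|---|---|
| SAP 2.1.4.4, chemistry list | Listed as a safety test | Count made |
| SAP 2.1.4.4, closing sentence | Called efficacy, sent to 2.4.4 | No safety table |
| SAP 2.1.3, 2.4.4, efficacy rows of Appendix D | Not mentioned | No efficacy table |
| SAP 2.4.5, common rules | No PCSA summary for protocol efficacy endpoints; names plasma glucose, not serum glucose | No count for FPG; unclear for serum glucose |
| SAP 2.4.5.4 | Covers the 2.1.4.4 groups and the Appendix B abnormalities | Count made |
| SAP Appendix B | Low-glucose criterion present | Count made |
| Protocol Table 2, 11.4.3, 11.4.3.5 | Safety test; PCSA count for each test | Count required |

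The other three parameters in the closing sentence do have an analysis. UACR is a secondary endpoint under SAP 2.4.4.2, and UGE and UGCR have by-visit summaries in Appendix D. Serum glucose alone has none.

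Two outcomes follow for serum glucose. If the closing sentence is followed and the 2.4.5 exclusion is carried over to it, neither an efficacy table nor a PCSA table appears. If the chemistry list, 2.4.5.4 and Appendix B are followed, the PCSA table appears. For FPG there is one outcome. It is a protocol efficacy endpoint, so 2.4.5 applies; it gets its ANCOVA and by-visit statistics, including the minimum, but no number of patients below a threshold.

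**Visit count** (protocol flow chart 1.2 and section 9.1.4.2; on-treatment visits after baseline, Visits 4 to 13)

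- Safety chemistry, including serum glucose: Visits 4 to 13 = 10
- FPG: Visits 7 to 13 = 7
- Scheduled visit-day self-monitoring (SMBG): Visits 6 to 13 = 8
- Serum glucose without FPG: 10 − 7 = 3 (Visits 4, 5, 6)
- Serum glucose with neither FPG nor visit-day SMBG: 2 (Visits 4, 5)

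With 276 patients and full attendance, the planned values are 10 × 276 = 2,760, of which 3 × 276 = 828 have no FPG beside them and 2 × 276 = 552 have neither. These are ceilings on values drawn, not counts of low values.

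Visit 14 also has serum glucose without FPG. At 4 weeks after the last dose it lies outside the 15-day TEAE window.

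**Self-monitoring**

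The protocol asks for fasting SMBG at least 3 times a week. To Week 26 that is 3 × 26 = 78 unmasked readings per patient, against 8 serum glucose values (Visits 4 to 11). Readings of ≤70 mg/dL go on the hypoglycaemia e-CRF page.

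**The case against.** The best defence is that the SAP already requires the count. The 2.4.5 exclusion covers protocol efficacy endpoints, and serum glucose is not one. It stays in the 2.1.4.4 chemistry list, and 2.4.5.4 orders the Appendix B abnormalities for that list. This defeats the stronger statement that a reader might infer, that laboratory-detected low glucose is counted nowhere and the Appendix B row is never produced. The text contradicts itself; it does not clearly omit the count. But the defence does not settle the matter, because a row in Appendix B is no guarantee of a table. That appendix is a general list for phase 2/3 studies, and its HbA1c row is one that 2.4.5 expressly suppresses.

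A second defence is that serum glucose in the closing sentence loosely means FPG, since the masking rule treats plasma and serum fasting glucose together. On that reading Section 2.4.4 does analyse it, but 2.4.5 then withholds the low-value count.

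A third is that SMBG is far more frequent than laboratory sampling, is unmasked, continues at home in Weeks 1 and 2, and feeds the e-CRF page. This stands. It would be wrong to say that low glucose has no route into the hypoglycaemia table. What has no described route is the low central-laboratory value itself. The DMC reviews unblinded safety data, but its analysis plan is a separate document and does not settle what the study report shows.

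**Conclusion.** The point holds as a conflict between stated rules, and the SAP should be corrected. SAP 2.1.4.4 (closing sentence) and 2.4.5 pull against the chemistry list in 2.1.4.4, SAP 2.4.5.4, Appendix B, and protocol Table 2 and 11.4.3.5. A safety count that the protocol requires is left to the programmer's reading. For FPG the absence of a threshold count is definite; for serum glucose it is undetermined.

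In scope, the conflict touches all 10 on-treatment serum glucose visits. It matters most at the 3 visits where serum glucose is the only central glucose, and especially at the 2 that also lack scheduled visit-day SMBG. The number of patients or low values affected cannot be given, because the documents contain no rate of low central glucose. Any such number would be assumption alone.

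The conclusion assumes that no unseen text, such as a redacted row of the SAP change tables, resolves the conflict. No efficacy inference is affected.

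**What to change.** Three edits to the SAP:

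1. In the closing sentence of 2.1.4.4, delete serum glucose, leaving UGE, UACR and UGCR.
2. In the common rules of 2.4.5, state as an explicit exception to the exclusion that the Appendix B low-glucose criterion (≤3.9 mmol/L and below LLN) is summarised by treatment group over the TEAE period for central-laboratory serum glucose.
3. In the same place, state whether FPG is included in that count.

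Show the table separately from the e-CRF hypoglycaemia table. The two also use different windows after the last dose (15 days for laboratory values, 1 day for hypoglycaemia), which a footnote should say. A further row at <3.0 mmol/L, and a listing of low values with no matching e-CRF event, are optional; the protocol does not require them for laboratory data. Masking and site alerts stay as they are.

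The cost is wording and one descriptive table from data already collected. A low reading may appear in both tables, which is harmless because they are not added together. SAP 1.6 says that the first-step analysis has already been run for top-line results, so the edit should be dated and its reason recorded. No test or alpha is involved.

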2.1.4.5 Vital signs variables

Vital signs include: heart rate, systolic and diastolic blood pressure, temperature, and respiratory rate (see study flowchart in [Appendix E](#) for designated visits). They will be performed after the patient has been seated for at least 5 minutes. Blood pressure and HR will be assessed 3 times with at least 1 minute between each measurement following the 5-minute rest period. The mean of the 3 measurements will be analyzed for each vital sign variable (HR, SBP, and DBP).

2.1.4.6 Physical examination

A complete physical exam will be performed at Visit 1 (Screening), Visit 11 (Week 26) and Visit 13 (Week 52). “Normal”, “Abnormal” or “Not done” as determined by the Investigator will be reported in the e-CRF by body system.

2.1.4.7 Electrocardiogram variables

12-lead ECG record is performed locally at Visit 2 (Run-in), Visit 11 (Week 26), and Visit 13 (Week 52). ECG status of “normal” or “abnormal” will be reported in the e-CRF as determined by the investigator.

2.1.5 Pharmacokinetic variables

Pharmacokinetic variables include the concentration of sotagliflozin and its 3-O-glucuronide metabolite in the sotagliflozin group (see study flowchart in [Appendix E](#) for designated visits).

